6.1 Risks

The procedures involved in this research (i.e., online assessments, online intervention) are considered low-risk. Thus, participants will incur minimal risks due to their participation in this study. Potential untoward events that may occur include:

- Emotional discomfort.
- Breach of confidentiality.

The level of risk for each of these events is minimal.

Emotional discomfort. Some of the topics that are asked about or discussed (e.g., SEOM use, sexual behaviors) may cause discomfort or anxiety. There is also the potential for anxiety related to acknowledging behavior with potential legal implications (alcohol/drug use, condomless sex which placed someone at risk of contracting an infectious disease).

These risks are recognized. Nonetheless, recent research assessing the psychological impact of similar questions among LGBT adolescents found that 90% of the participants reported feeling “very comfortable” or “comfortable” with the questions they were asked and only 3% reported feeling “very uncomfortable,” which is similar to what has been found in other research assessing reactions to questions about sexuality and substance use.^{58,59}

To minimize the potential for participant psychological distress or discomfort during the online assessments and intervention participants will be notified that they can skip any questions or intervention content that they are uncomfortable with and stop the assessment or intervention at any time. Participants will also be invited to contact the PI should any discomfort arise.

Breach of confidentiality. The study will take every precaution to ensure that the privacy of study participants is protected. To guard confidentiality, each participant will receive a unique ID number. All computer records will be protected by standard measures that limit data access to authorized personnel. Online data will be collected and managed using the REDCap⁶⁰ electronic data capture tools managed by Boston University Medical Campus IT. REDCap is a secure, web-based application designed by network engineering and approved by IT Security. REDCap servers are backed up daily and monitored for hardware failures. Self-report and usage data will be collected from respondents, and likewise retrieved by the PI, over an SSL encrypted connection.

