Other considerations: Mental health and substance use. As mental health and substance use issues are prevalent among ASMM, we will provide all participants with links and phone numbers for LGBT-specific services (e.g., the National Alliance on Mental Health LGBTQ website, PRIDE Institute Substance Use Treatment website, GLBT National Youth Talkline phone number, Trevor Helpline Crisis Intervention for LGBTQ Youth phone number). Although none of the proposed measures specifically ask about reportable issues, the satisfaction survey for the intervention will include open-ended responses. The PI will check these open-ended responses daily in the unlikely event that a participant reports any indication of current, ongoing abuse or neglect of children or elders and/or of imminent danger to self or a specified individual as these indications will have to be considered for clinical intervention and mandated reporting to the appropriate authorities. Daily checks will be documented via PI initials on a study calendar.

Other considerations: Website developer training. To ensure the website developer is informed of research ethics and participant confidentiality they have completed on-line CITI Human Subjects Protection training and signed an

agreement to keep all participant information confidential. The developer has a background in designing/programming websites for research purposes, thus have completed these trainings and signed research confidentiality agreements before.

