- **Recruitment, screening, and assent (described in more detail below):** Participants will be recruited via online advertisements. Once they click on an advertisement they will be presented with information about the study and a brief online screener to establish eligibility. If they are eligible they will be presented with assent materials and complete capacity to assent questions. If they agree to participate they will then be emailed a unique link to the baseline assessment.
- **Baseline assessment:** Participants will be sent an email with a link to a self-report online survey ($N = 150$; Approx. 25-35 minutes); compensation for time (\$15 electronic gift card via email). If participants do not complete the baseline assessment within three days of assenting, we will send them up to 3 reminder emails in a 10-day period.
- **Randomization:** immediately following the final question in the baseline assessment, REDCap⁶⁰ will be programmed to randomly assign participants (1:1 randomization) to the YM&M intervention or to a control group. The randomization schedule will be generated using a permuted block randomization procedure with small, randomized blocks.
 - Participants randomized to the YM&M ($n = 75$) intervention will be sent an email with username (their email) and a temporary password and asked to complete all of the website content within three weeks of receiving the email. Participants will be asked at first log-in to set up their own password. If a participant has not logged into the website within one week of receiving the original email, they will be sent up to 3 reminder emails in a 10-day period.
 - Participants in the control condition ($n = 75$) will be sent an email with links to various HIV prevention websites (e.g., the CDC HIV Prevention site, the National HIV and STD Testing Resource site) and encouraged to visit at least one site in the next three weeks.
- **YM&M intervention exposure:** Intervention content, language, and length was informed by a youth advisory board and a previously completed online survey.^{24,26,45,45-47} Although the intervention is designed to be completed in one sitting (i.e., < 90 minutes in length), participants will be given the option of logging out and logging in again to continue where they left off, should they need to. Intervention content is described in more detail above and in Appendix 3.

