- **Post-intervention assessment:** Three weeks after the baseline survey participants will be sent an email to complete a second online survey ($N = 150$; Approx. 15-25 minutes); compensation for time (\$25 electronic gift card via email). If participants do not complete the post-intervention assessment within three days of receiving the email, we will send them up to 3 reminder emails in a 10-day period.
- **Follow-up assessment:** Fifteen weeks after the baseline survey participants will be sent an email to complete a final online survey ($N = 150$; Approx. 20-30 minutes); compensation for time (\$35 electronic gift card via email). If

participants do not complete the follow-up assessment within three days of receiving the email, we will send them up to 3 reminder emails in a 10-day period.

- **All participants:** Participants will be offered a bonus if they complete all assessments (\$20 electronic gift card via email). All participants will receive a list of youth-oriented resources at the end of the survey or if they are ineligible (Appendix 4).

Detailed description of recruitment, screening, assent, and retention procedures.

Recruitment Processes. Participants will be recruited using advertisements and posts on social networking websites (e.g., Facebook, Instagram, Snapchat). Potential participants recruited via advertisements will be directed to the screening website which will assent them for screening and then ask potential participants to continue on for eligibility questions.

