Assent procedures for the full study will describe the study, its risk and benefits, confidentiality, no deception, and how to contact the investigators. The assent process will highlight that potential participants have the option of refusing to participate in the study, withdrawing their participation at any time, and/or refusing to answer any questions that they feel uncomfortable responding to. Further, potential participants will be informed that their decision to participate or not participate in the study will not affect their relationship with any websites, LGBT youth-oriented CBOs, clinics, or Boston University. Capacity to assent will be further confirmed by administering multiple choice questions that will evaluate participants' ability to: (1) name things they will be expected to do during the study, (2) explain how they will be assigned to their group, (3) explain what they would do if they experienced distress during the study, and (4) identify potential risks for participating in the study.^{85,86} Participants who are unable to accurately answer the multiple choice questions will be redirected to the relevant portions of the assent materials and asked the questions again. Capacity to assent questions and answers will be automatically re-ordered each time they are presented to reduce the chance of participants blindly choosing answers until they get the right ones. Participants will be given three chances to correctly answer capacity to assent materials. If after three chances they continue to answer questions incorrectly they will be considered ineligible. Potential participants will be given the option of contacting study staff (via e-mail, telephone number, and mailing address) to ask questions before enrolling. After potential participants have been determine to have capacity to assent they will be asked whether they would like to participate in the study or not, which is the documentation of their decision to enroll in the study. Once eligible participants have assented they will be sent an email containing a unique link to the baseline survey. To proceed to the main body of the survey, eligible participants will be required to click on that link. Participants will be reminded about assent parameters at the start of each follow-up assessment.

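### Minor participant-protection point: an assented youth who stops partway through baseline reaches neither delivery point that section 9 states for the resource list, although section 6.1 promises support links to everyone taking part

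*Combined protocol and SAP*

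**What the plan says.** The combined protocol and SAP deals with support resources in two places.

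- Section 6.1, under mental health and substance use, makes the promise and gives its reason: "As mental health and substance use issues are prevalent among ASMM, we will provide all participants with links and phone numbers for LGBT-specific services". It states no timing or route and does not cite Appendix 4.
- Section 9, in the item on all participants, gives the timing of the Appendix 4 list: "All participants will receive a list of youth-oriented resources at the end of the survey or if they are ineligible".

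Three other statements decide who is covered.

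- Section 6.1, on emotional discomfort, says youths will be told "they can skip any questions or intervention content that they are uncomfortable with and stop the assessment or intervention at any time". They are also invited to contact the principal investigator (PI).
- Section 9 applies the word participant to youths who have assented but not finished baseline, in the clause "If participants do not complete the baseline assessment within three days of assenting". Its assent paragraph places enrolment at the youth's agreement, before the baseline link is sent.
- Section 9 places randomisation "immediately following the final question in the baseline assessment".

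**The concern.** Section 6.1 justifies the support links by the prevalence of mental health and substance use problems in this group. Baseline is where the study first asks about both: section 11.2 and its Table 3 place the CAGE-AID, the PHQ-4 and the sexual abuse subscale of the Childhood Trauma Questionnaire there. A youth upset by such items may use his right to stop, and by stopping he moves away from the point at which section 9 says the list is given. Meanwhile, someone found ineligible, who may have seen no more than a brief screener, does receive it.

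These are 14- to 17-year-olds taking part under a requested waiver of parental consent. The other stated responses to discomfort are to skip, to stop or to contact the PI. A list of outside services helps without contact with study staff, so it matters most to a youth who leaves without writing to anyone. What is at stake is protection of a few participants, not the validity of any result.

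**Working it through.** No formula applies, and the plan gives no figure to reproduce. The check follows one youth through the stated steps.

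1. **Is he a participant?** Yes. He has passed the capacity questions and agreed to take part, which section 9 treats as enrolment. The reminder-email text in section 9 also calls baseline non-completers participants. The section 6.1 promise therefore covers him.
2. **May he stop partway?** Yes, under section 6.1.
3. **Does either stated delivery point reach him?** He has not reached the end of the survey, and he was found eligible. Neither does.
4. **Does randomisation bring him other material?** No. It follows the last baseline question, so he receives neither the intervention login nor the control-arm links.
5. **Do the reminder emails reach him with the list?** He may get up to 3 in a 10-day period, but they are not said to carry it. Section 6.1 requires correspondence to give no hint of the study's content, so it cannot be assumed that they do.
6. **Does the daily check of open-ended answers pick him up?** No. Section 6.1 ties that check to the satisfaction survey, which is given at post-intervention.
7. **Has he seen support numbers earlier?** Unknown. Section 9 summarises the assent content as follows: "Assent procedures for the full study will describe the study, its risk and benefits, confidentiality, no deception, and how to contact the investigators". The list is not named there, but a one-sentence summary is weak evidence about pages that are not in the supplied text.
8. **Are randomised youths missed?** Not on the natural reading. The assent paragraph of section 9 uses the word survey for the baseline questionnaire, and every randomised youth has reached its end. That gives 0 of 150.

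Sections 6.1 and 9 do not contradict each other. One makes a promise without timing, the other gives timing, and the timing as written leaves out a case that the protocol itself foresees.

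**The case against.** The strongest reply is that the assent pages may already close the gap. Before baseline, each youth must show that he can "explain what they would do if they experienced distress during the study", and one who answers wrongly is sent back to the relevant assent material. The assent text therefore says something about distress, and phone numbers could well be there. This stands: the absence of those pages from the supplied text is not a defect in the plan, and the point has to be conditional on what they contain.

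Second, a reader might infer that section 9 restricts the list to those two moments. It does not say so. Both sections say that all participants will get the resources, and nothing suggests an intention to leave anyone out. Nor is it stated that the section 6.1 links are the Appendix 4 list; they could be delivered by another route. Both qualifications stand. What remains is that no such route is described.

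Third, section 5 uses the phrase all participants for the 150 who complete baseline, and on that usage the promise is met. This does not answer the point, because section 9 treats assented non-completers as enrolled participants.

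Fourth, a distressed youth can skip items and still reach the end, or contact the PI, and the order of items within baseline is not given, so he may not have met the sensitive ones. These facts reduce the risk but do not supply a delivery step for a youth who stops and stays silent.

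**Conclusion.** The point holds as a minor, cheap improvement: the delivery rule as stated does not reach every participant to whom support links are promised. It assumes that the survey in section 9 means baseline, that the section 6.1 links are the Appendix 4 list, and that the assent pages do not already show the numbers. If the last assumption fails, a cross-reference is all that is needed.

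The number affected cannot be estimated. A reader might take the 3% of LGBT adolescents whom section 6.1 reports as very uncomfortable with similar questions and turn it into a count. If all of them stopped for good while 150 others completed baseline, that would give 150 × 0.03 / 0.97 = 4.6 youths; if half did, 150 × 0.015 / 0.985 = 2.3; if none did, 0. The documents do not support reading this as a size. The 3% measures discomfort in other research, not stopping in this study; the shares of all, half and none are invented; and youths who stop for other reasons are left out.

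There is no effect on the sample size, the outcomes or the analysis.

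**What to change.** Amend the section 9 sentence along these lines: every assented youth is shown the mental-health, substance-use and crisis contacts named in section 6.1 before the baseline questions begin, at assent or on the first baseline page, under a neutral label; the full Appendix 4 list continues to be given at the end of the survey and to anyone found ineligible.

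Tying the early page to the contacts in section 6.1 avoids having to divide Appendix 4, whose contents are not in the supplied text. It also keeps any HIV/STI information on the list until after the baseline knowledge items. Placing the page before the questions reaches every youth who opens baseline, wherever he stops. If the assent pages already carry these contacts, section 9 need only say so.

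The cost is one sentence, at most one static REDCap page and a minor IRB amendment, with no extra staff or participants. The downside is one more page that another person might see, hence the neutral label, in keeping with the privacy measures in section 6.1.

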10.1 Definitions

The following definitions will be used in the assessment of safety:

Adverse Events (AEs) include any abnormal or harmful behaviors, increasing risk behaviors (e.g., sexual risk behaviors), suicidal behaviors, breach in the protection of participant data or breach of confidentiality whether or not consider related to the subjects participation in the research.

Serious Adverse Event (SAE) is any adverse event that

- (1) results in death;
- (2) is life-threatening;
- (3) results in inpatient hospitalization or prolongation of existing hospitalization;
- (4) results in a persistent or significant disability/incapacity;
- (5) results in a congenital anomaly/birth defect; or
- (6) based upon appropriate medical judgment, may jeopardize the subject's health and may require medical or surgical intervention to prevent one of the other outcomes listed in this definition (examples of such events include allergic bronchospasm requiring intensive treatment in the emergency room or at home, blood dyscrasias or convulsions that do not result in inpatient hospitalization, or the development of drug dependency or drug abuse).

Life-threatening means that the event places the subject at immediate risk of death from the event as it occurred.

Unanticipated Problem is defined as an event, experience or outcome that meets **all three** of the following criteria:

- is unexpected; AND
- is related or possibly related to participation in the research; AND
- suggests that the research places subjects or others at a greater risk of harm (including physical, psychological, economic, or social harm) than was previously known or recognized.

	Data Source / Frequency of Aggregation	Frequency of Review
Data Type	Online Assessments/Website	PI
Accrual, Retention, and Attrition	Daily	Daily
Adverse Events*	Daily	Daily
Missing data/data integrity	Twice a Week	Twice a Week
Intervention Integrity	Daily	Daily
* Please note: serious adverse events will be reported within 24 hours to the IRB and to the sponsor (NIH) in accordance with their requirements.		

Possibly related means there is a reasonable possibility that the incident, experience, or outcome may have been caused by the procedures involved in the research

Unexpected means the nature, severity, or frequency of the event is not consistent with either:

- the known or foreseeable risk of adverse events associated with the procedures involved in the research that are described in (a) the protocol-related documents, such as the IRB-approved research protocol, any applicable investigator brochure, and the current IRB-approved informed consent document, and (b) other relevant sources of information, such as product labeling and package inserts; or
- the expected natural progression of any underlying disease, disorder, or condition of the subject(s) experiencing the adverse event and the subject’s predisposing risk factor profile for the adverse event.

10.2 Safety Review

Both the risks listed in Section 4.1 and unknown risks will be monitored as follows:

Study safety and progress will be monitored according to the schedule outlined in Table 2 (and more frequently, if needed). The PI ([name]), will closely supervise all study activities on a day-to-day basis. The PI will personally monitor recruitment procedures, accrual and retention, and data integrity daily in order to take the necessary measures in a timely fashion. Participants will be instructed to notify the PI immediately if any symptoms occur during the online assessments or sexual health media literacy intervention. All AEs will be documented daily by the PI. AEs will be labeled according to severity, as ‘mild’ if the event does not have a major impact on the participant, ‘moderate’ if it causes the participant some minor inconvenience and ‘severe’ if it causes a substantial disruption to the participant’s well-being. All AEs and SAEs will be labeled as definitely, probably, possibly or unrelated to the study intervention.

10.3 Reporting Plans

The Principal Investigator at BMC/BU Medical Campus will report Unanticipated Problems, safety monitors' reports, and Adverse Events to the BMC/BU Medical Center IRB in accordance with IRB policies:

- Unanticipated Problems occurring at BMC/BU Medical Campus will be reported to the IRB within 7 days of the investigator learning of the event.
- Reports from safety monitors with recommended changes will be reported to the IRB within 7 days of the investigator receiving the report.
- Adverse Events (including Serious Adverse Events) will be reported in summary at the time of continuing review, along with a statement that the pattern of adverse events, in total, does not suggest that the research places subjects or others at a greater risk of harm than was previously known.
- Reports from safety monitors with no recommended changes will be reported to the IRB at the time of continuing review.

The PI will promptly inform the NIH and the IRB of any changes in recruitment or in the protocol relevant to safety as the study is being performed. She will additionally notify the NIH promptly of any unanticipated problems or any actions taken by the IRB during continuing study review and any major changes in the status of the ongoing protocol which would only occur with IRB approval. Such changes would include but are not limited to: amendments to the protocol, temporary suspension of participant accrual, or of the protocol, any changes in informed consent or IRB approval status, termination of participant accrual or of the protocol, or other problems or issues that could affect the human subjects in the study.

